### **14.3.2 Secondary Efficacy Outcome Measures**

The secondary endpoint is the proportion of subjects successfully achieving abstinence from cocaine during the last three weeks of treatment (Study Weeks 11-13) in the subset of the PPEE population who are also part of the Non-Drinker Population or the AAA Population. Comparison of this proportion in subjects receiving lorcaserin vs. placebo will constitute the secondary endpoint analysis. Abstinence will be defined as described for the primary endpoint.

### **14.3.3 Exploratory Outcome Measures**

- a) The proportion of subjects successfully achieving abstinence from cocaine during the last three weeks of treatment (Study Weeks 11-13) in the ITT population. Comparison of this proportion in subjects receiving lorcaserin vs. placebo will constitute the analysis. Abstinence will be defined as described for the primary endpoint. (Note: what the primary endpoint would have been if there were no enrichment strategy)
- b) The proportion of subjects successfully achieving abstinence from cocaine during the last three weeks of treatment (Study Weeks 11-13) in the subset of the ITT population who are also part of the Non-Drinker population or the AAA Population. Comparison of this proportion in subjects receiving lorcaserin vs. placebo will constitute the analysis. Abstinence will be defined as described for the primary endpoint. (Note: what the secondary endpoint would have been if there were no enrichment strategy)
- c) The proportion of subjects successfully achieving abstinence from cocaine during the last three weeks of treatment (Study Weeks 11-13) in the non-PPEE population. Comparison of this proportion in subjects receiving lorcaserin vs. placebo will constitute the analysis. Abstinence will be defined as described for the primary endpoint.
- d) The proportion of subjects successfully achieving abstinence from cocaine during the last three weeks of treatment (Study Weeks 11-13) in the subset of the non-PPEE population who are also part of the Non-Drinker population or the AAA Population. Comparison of this proportion in subjects receiving lorcaserin vs. placebo will constitute the analysis. Abstinence will be defined as described for the primary endpoint.
- e) The proportion of subjects successfully achieving abstinence from cocaine during the last three weeks of treatment (Study Weeks 11-13) in the Baseline Low Use/Adherent Population. Comparison of this proportion in subjects receiving lorcaserin vs. placebo will constitute the analysis. Abstinence will be defined as described for the primary endpoint. (Note: similar to primary endpoint but in subjects excluded from the PPEE population only because of low baseline cocaine use)
- f) The proportion of subjects successfully achieving abstinence from cocaine during the last three weeks of treatment (Study Weeks 11-13) in the subset of the Baseline Low Use/Adherent Population who are also part of the Non-Drinker population or the AAA Population. Comparison

of this proportion in subjects receiving lorcaserin vs. placebo will constitute the analysis. Abstinence will be defined as described for the primary endpoint. (Note: similar to secondary endpoint but in subjects excluded from the PPEE population only because of low baseline cocaine use)

g) The proportion of subjects successfully achieving abstinence from cocaine during the last three weeks of treatment (Study Weeks 11-13) in the Baseline Adherent Population. Comparison of this proportion in subjects receiving lorcaserin vs. placebo will constitute the analysis. Abstinence will be defined as described for the primary endpoint. (Note: what the primary endpoint would have been if low baseline cocaine use had not excluded subjects from the PPEE Population)

h) The proportion of subjects successfully achieving abstinence from cocaine during the last three weeks of treatment (Study Weeks 11-13) in the subset of the Baseline Adherent Population who are also part of the Non-Drinker population or the AAA Population. Comparison of this proportion in subjects receiving lorcaserin vs. placebo will constitute the analysis. Abstinence will be defined as described for the primary endpoint. (Note: what the secondary endpoint would have been if low baseline cocaine use had not excluded subjects from the PPEE Population)

i) The proportion of subjects successfully achieving abstinence from cocaine during the last three weeks of treatment (Study Weeks 11-13) in the subset of the AiView Users Population who are also part of the PPEE Population. Comparison of this proportion in subjects receiving lorcaserin vs. placebo will constitute the analysis. Abstinence will be defined as described for the primary endpoint.

j) The proportion of subjects successfully achieving abstinence from cocaine during the last three weeks of treatment (Study Weeks 11-13) in the subset of the AiView Non-Users Population who are also part of the PPEE Population. Comparison of this proportion in subjects receiving lorcaserin vs. placebo will constitute the analysis. Abstinence will be defined as described for the primary endpoint.

k) The proportion of subjects successfully achieving abstinence from alcohol during the last three weeks of treatment (Study Weeks 11-13) in the subset of the AAA Population who are also in the Baseline Adherent Population and who received a diagnosis of Alcohol Use Disorder (AUD) during screening. Comparison of this proportion in subjects receiving lorcaserin vs. placebo will constitute the analysis. A subject will be regarded as abstinent from alcohol during the last three weeks of treatment if:

- There are self-report data indicating no alcohol use on each day of the 3-week period;
- There is at least one ethyl glucuronide (EtG) assay result for a urine sample collected within the 3-week period; and
- EtG assay results are negative (EtG < 500 ng/mL) for all urine samples collected during the 3-week period.

Subjects not meeting these three criteria (including dropouts) will be regarded as having failed to achieve abstinence from alcohol.

- l) The proportion of subjects successfully achieving abstinence from alcohol during the last three weeks of treatment (Study Weeks 11-13) in the subset of the AAA Population who are also in the Baseline Adherent Population. Comparison of this proportion in subjects receiving lorcaserin vs. placebo will constitute the analysis. Abstinence from alcohol will be defined as described above. (Note: attempting alcohol abstinence and good baseline adherence +/- AUD)
- m) The proportion of subjects successfully achieving abstinence from alcohol during the last three weeks of treatment (Study Weeks 11-13) in the subset of the AAA Population who received a diagnosis of AUD during screening. Comparison of this proportion in subjects receiving lorcaserin vs. placebo will constitute the analysis. Abstinence from alcohol will be defined as described above. (Note: attempting alcohol abstinence with AUD +/- good baseline adherence)
- n) The proportion of subjects successfully achieving abstinence from alcohol during the last three weeks of treatment (Study Weeks 11-13) in the subset of the ITT Population who received a diagnosis of AUD during screening. Comparison of this proportion in subjects receiving lorcaserin vs. placebo will constitute the analysis. Abstinence from alcohol will be defined as described above. (Note: includes all subjects with AUD whether or not trying to abstain from alcohol)
- o) The proportion of subjects successfully achieving abstinence from alcohol during the last three weeks of treatment (Study Weeks 11-13) in the ITT Population. Comparison of this proportion in subjects receiving lorcaserin vs. placebo will constitute the analysis. Abstinence from alcohol will be defined as described above.
- p) The proportion of subjects in the ITT Population reporting no alcohol use for each day of the last three weeks of treatment (Study Weeks 11-13). Comparison of this proportion in subjects receiving lorcaserin vs. placebo will constitute the analysis. (Note: comparison with results for the endpoint described immediately above will provide an indication of the extent to which subjects under-reported their alcohol use and falsely claimed alcohol abstinence at the end of the study)
- q) The proportion of subjects successfully achieving abstinence from cocaine during the last three weeks of treatment (Study Weeks 11-13) in the subset of the PPEE Population who completed the Treatment Phase (remaining through the end of Study Week 13) and were abstinent from alcohol during the last three weeks of treatment. Comparison of this proportion in subjects receiving lorcaserin vs. placebo will constitute the analysis. Abstinence from cocaine will be defined as described for the primary endpoint, and abstinence from alcohol will be defined as described above.
- r) The proportion of subjects successfully achieving abstinence from cocaine during the last three weeks of treatment (Study Weeks 11-13) in the ) in the subset of the PPEE Population who completed the Treatment Phase (remaining through the end of Study Week 13) and were NOT abstinent from alcohol during the last three weeks of treatment. Comparison of this proportion in subjects receiving lorcaserin vs. placebo will constitute the analysis. Abstinence from cocaine will be defined as described for the primary endpoint, and abstinence from alcohol will be defined as described above.

s) The proportion of subjects successfully achieving abstinence from cocaine during the last six weeks of treatment (Study Weeks 8-13) in the PPEE population. Comparison of this proportion in subjects receiving lorcaserin vs. placebo will constitute the primary endpoint analysis.

A subject will be regarded as a treatment success (abstinent from cocaine during the last six weeks of treatment) if:

- There are self-report data indicating no cocaine use on each day of the 6-week period;
- There is at least one benzoylecgonine (BE) assay result for a urine sample collected within the 6-week period; and
- BE assay results are negative ( $BE < 150 \text{ ng/mL}$ ) for all urine samples collected during the 6-week period.

Subjects not meeting these three criteria (including dropouts) will be regarded as treatment failures.

t) The proportion of subjects successfully achieving abstinence from alcohol during the last six weeks of treatment (Study Weeks 8-13) in the subset of the AAA Population who are also in the Baseline Adherent Population and who received a diagnosis of Alcohol Use Disorder (AUD) during screening. Comparison of this proportion in subjects receiving lorcaserin vs. placebo will constitute the analysis. A subject will be regarded as abstinent from alcohol during the last six weeks of treatment if:

- There are self-report data indicating no alcohol use on each day of the 6-week period;
- There is at least one ethyl glucuronide (EtG) assay result for a urine sample collected within the 6-week period; and
- EtG assay results are negative ( $EtG < 500 \text{ ng/mL}$ ) for all urine samples collected during the 6-week period.

Subjects not meeting these three criteria (including dropouts) will be regarded as having failed to achieve abstinence from alcohol.

u) The proportion of subjects in the [subset of the Baseline Adherent Population with at least one lorcaserin plasma assay result] whose lorcaserin plasma levels were in the expected range for all assay results (expected range to be specified in Statistical Analysis Plan).

v) The proportion of subjects in the [subset of the Baseline Non-Adherent Population with at least one lorcaserin plasma assay result] whose lorcaserin plasma levels were in the expected range for all assay results (expected range to be specified in Statistical Analysis Plan).

- w) The proportion of subjects in the [subset of the PPEE Population with at least one lorcaserin plasma assay result] whose lorcaserin plasma levels were in the expected range for all assay results (expected range to be specified in Statistical Analysis Plan).
- x) The proportion of subjects in the [subset of the Non-PPEE Population with at least one lorcaserin plasma assay result] whose lorcaserin plasma levels were in the expected range for all assay results (expected range to be specified in Statistical Analysis Plan).

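### The gap between alcohol endpoints (p) and (o) mixes missing EtG results with urine-contradicted self-report, yet the plan reads it as under-reporting

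*Combined protocol and SAP*

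**What the plan says.** Section 14.3.3, item (o), is alcohol abstinence in Weeks 11-13 in the ITT Population: "Abstinence from alcohol will be defined as described above". The definition it points back to stands under item (k) and has three parts:

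- The subject's own report shows no drinking on any day of the window.
- A urine result exists: "There is at least one ethyl glucuronide (EtG) assay result for a urine sample collected within the 3-week period".
- No result is positive: "EtG assay results are negative (EtG < 500 ng/mL) for all urine samples collected during the 3-week period".

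It closes with the rule for everyone else: "Subjects not meeting these three criteria (including dropouts) will be regarded as having failed to achieve abstinence from alcohol".

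Item (p) takes the same population and window but asks only for reported non-use on each day. It has no EtG requirement. Its note says that "comparison with results for the endpoint described immediately above will provide an indication of the extent to which subjects under-reported their alcohol use", and goes on to name false claims of abstinence at the end of the study.

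The two data sources are collected differently. Alcohol use is logged daily on a handheld device (Sections 11.5 and 12.24), and days that the device did not capture are filled by Timeline Followback (Section 12.26). EtG is an on-site urine test stick (Section 12.19), scheduled at each weekly visit (Table 3).

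**The concern.** The note treats every subject who passes (p) and fails (o) as someone whose report was untrue. A subject can also fall into that gap because no EtG result exists for Weeks 11-13. Self-report can be completed away from the clinic or filled in afterwards, while EtG needs a visit, so a full self-report with no EtG result is possible under the plan. For such a subject, nothing in the urine data speaks against the report.

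At stake is the validity of one stated interpretation. If the comparison is used as the note describes, absent urine data enter the figure offered as the extent of under-reporting.

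**Working it through.** The plan gives no figure on this point to reproduce. The check is algebra on the two definitions, followed by illustrations with assumed inputs.

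**Decomposition.** Let

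- S = share of ITT subjects meeting (p);
- m = share of those with no EtG result in Weeks 11-13;
- f = share, among those with a result, with at least one positive EtG.

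A subject meets (o) only by meeting (p), having a result, and having no positive result. Hence

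(o) = S(1 − m)(1 − f)

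(p) − (o) = S[m + (1 − m)f] = S·m + S(1 − m)f

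The term S(1 − m)f is self-report contradicted by EtG. The term S·m is missing urine. A subject lacking self-report for any day fails both endpoints and does not enter the gap.

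**Missing urine as a share of the gap** = m / [m + (1 − m)f]. S cancels. The documents give neither m nor f, so both are assumptions:

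| m | f = 5% | f = 10% | f = 20% |
|---|---|---|---|
| 2% | 29% | 17% | 9% |
| 5% | 51% | 34% | 21% |
| 10% | 69% | 53% | 36% |
| 20% | 83% | 71% | 56% |

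For example, at m = 5% and f = 10%: 0.05 / (0.05 + 0.95 × 0.10) = 0.05 / 0.145 = 34%.

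**In subjects.** Section 14.1 plans 272 enrolled and expects about 5% to drop out before randomization, so ITT is about 272 × 0.95 = 258. Assume S = 40% and f = 10%.

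- m = 5%: gap 0.40 × 0.145 = 5.8 points, about 15 subjects, of whom about 10 have a positive EtG and 5 have no result.
- m = 20%: gap 0.40 × (0.20 + 0.80 × 0.10) = 11.2 points, about 29 subjects, of whom about 8 have a positive EtG and 21 have no result.

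**Direction against true under-reporting.** Let D be the share of self-reported abstainers who in fact drank, and se the chance that a tested drinker has a positive EtG (assumed). Suppose also that missing EtG is unrelated to drinking and that non-drinkers never test positive. Then gap/S = m + (1 − m)·D·se, to be compared with D. With D = 20%:

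| se | m | gap/S | error against D |
|---|---|---|---|
| 1.0 | 5% | 24.0% | +4.0 points |
| 0.8 | 5% | 20.2% | +0.2 points |
| 0.5 | 5% | 14.5% | −5.5 points |
| 0.5 | 20% | 28.0% | +8.0 points |

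The sign is not fixed.

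**The case against.** The affected group may be small. To enter the gap without a urine result, a subject needs reported non-use for all 21 days and no EtG result at any visit in the window, and one result in three scheduled visits is enough. Ordinary dropouts with incomplete self-report fail both endpoints. In-clinic self-report, drug dispensing and device rewards are tied to the visits at which EtG is collected, and Section 11.12 adds a $40 bonus for attending all of Weeks 11-14. Nothing in the documents supports a missing share of 10% or 20%. The note claims only to give an indication, and (p) is one of 29 exploratory items. All of this stands. It limits the importance of the point but does not change what the gap contains.

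A reader might go further and infer that the comparison overstates under-reporting. The documents do not support that. A single negative EtG at the 500 ng/mL cut-off is enough to verify 21 days, so drinking that the test misses narrows the gap. Some subjects with no result may also have drunk.

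Two other inferences are tempting. One is that a positive first sample may reflect drinking before the window; that needs an EtG detection time, and Section 12.19 gives only a cut-off. The other is that the gap will colour the reading of self-report in the cocaine endpoint; no section uses it that way, and Section 14.3.1 has its own criteria based on benzoylecgonine.

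**Conclusion.** The point holds as a matter of definition: the (p)-(o) difference adds EtG-contradicted self-report to self-report with no EtG result, and it exceeds the EtG-contradicted share whenever the second group is not empty. The note should not present the whole difference as a gauge of false claims.

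The size cannot be stated, because m and f are not in the documents. Under the assumed ranges, missing urine is anywhere from 9% to 83% of the gap, so even a small missing fraction can matter when few tested subjects are positive. No claim is made about the net direction against true under-reporting. This is a minor, nearly free improvement to an exploratory measure; the primary and secondary analyses are not touched.

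**What to change.** Keep (o) and (p) as defined. Replace the note to (p) with a by-arm report of the share with any positive EtG among ITT subjects who self-report no alcohol on every day of Weeks 11-13 and have at least one EtG result in that period. Count self-reported abstainers with no EtG result separately, also by arm. Label the first quantity EtG-contradicted self-report, not total under-reporting, since it does not capture drinking that the test misses.

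The plan already uses this kind of restriction: items (u) to (x) limit the denominator to subjects with at least one lorcaserin plasma result. The cost is one sentence in the analysis plan and one extra table row. No new data are needed.

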**EFFICACY ASSESSMENTS:** An enrichment strategy based on pre-randomization data from the run-in phase will be used to define a subpopulation of study participants who are likely to be medication adherent during the Treatment Phase and who are likely to exhibit a low placebo response rate. Data from only this subpopulation, termed the “prequalified for primary efficacy endpoint” (PPEE) population, will be utilized for the primary endpoint success/failure analysis. The PPEE population consists of subjects who have demonstrated adherence to the acetazolamide run-in regimen (based on the plasma sample collected on Study Day 8) and who, on the first day of Screening, reported 8 or more days of cocaine use in the previous 30 days. The primary endpoint is the percentage of subjects successfully achieving abstinence from cocaine during the last three weeks of treatment (Study Weeks 11-13) in the PPEE population.

At the beginning of Study Day 1, at each weekly clinic visit from Week 1 through Week 14, and at the Week 16 Follow-Up Visit, data for the efficacy endpoints will be collected (including urine BE, cotinine and alcohol).

A subject will be regarded as a treatment success (abstinent from cocaine during the last three weeks of treatment) if:

- a. There are self-report data indicating no cocaine use on each day of the 3-week period;
- b. There is at least one benzoylecgonine (BE) assay result for a urine sample collected within the 3-week period; and
- c. BE assay results are negative (BE <150 ng/mL) for all urine samples collected during the 3-week period.

Subjects not meeting these three criteria (including dropouts) will be regarded as treatment failures.

The secondary endpoint is the proportion of subjects who successfully achieve abstinence from cocaine during the last three weeks of treatment (Study Weeks 11-13) in the subset of the PPEE population who are either Non-Drinkers or who are attempting alcohol abstinence, as evidenced by their decision to continue viewing the alcohol intervention modules on Study Day 8. Comparison of this proportion in subjects receiving lorcaserin vs. placebo will constitute the secondary endpoint analysis. In the analysis, abstinence will be defined as described for the primary endpoint.

An important exploratory endpoint will focus on the efficacy of lorcaserin in facilitation of abstinence from alcohol based on self-reported drinking and urine ethyl glucuronide (EtG) assays.

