While 272 subjects will be enrolled in the current study, it is estimated that 180 subjects (approximately 90 subjects per group) will meet criteria for inclusion in the PPEE population. Assuming 6% and 20% success rates (for achieving abstinence from cocaine) during placebo and lorcaserin treatment, respectively, 90 subjects per group in the PPEE population would yield 80% power (Pearson’s Chi-square test for two proportions; two-sided comparison, alpha = 0.05). The assumption of 6% success in the placebo group is based on results from similar cocaine medication trials conducted by NIDA in the past, using the same definition of “success” (placebo group success rates have ranged from 0 to 9%). The goal of 20% success in the lorcaserin group would constitute slightly more than a three-fold increase in success compared to the expected placebo success rate. Such efficacy would be clinically meaningful. No medications are currently approved for the treatment of cocaine use disorder, but a 3-fold increase in quit rate (vs. placebo) would constitute greater efficacy than has been observed for FDA-approved smoking cessation medications. A recent meta-analysis of randomized, placebo-controlled smoking cessation trials (Eisenberg *et al.*, 2008) revealed that placebo and bupropion quit rates were 11% and 20%, respectively (16 trials), placebo and nicotine gum quit rates were 14% and 19%, respectively (22 trials), placebo and nicotine patch quit rates were 7.5% and 13%, respectively (30 trials), and placebo and varenicline quit rates were 15% and 26%, respectively (13 trials). For the current study, multiple factors were considered in estimating that 180 of the 272 enrolled subjects will qualify for inclusion in the PPEE population. Further explanation requires an understanding of enrichment strategy details.

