**Figure 3. Enrichment Strategy Study Design**

## 14.2 Definitions of Study Populations

- 1) The “Intent-to-Treat (ITT) Population” – All subjects who may have taken at least one dose of lorcaserin or placebo after randomization on Study Day 8. This includes all subjects who receive at least one bottle of study drug (lorcaserin or placebo) after randomization on Study Day 8, with the exception of any subjects who return the full bottle before leaving the clinic on Study Day 8 (this may occur, for example, if a subject changes his/her mind about continuing in the study).
- 2) The “PPEE Population” – The subset of the ITT Population who prequalify for the primary efficacy endpoint by meeting the specified PPEE criteria prior to randomization.
- 3) The “Non-PPEE Population” – The subset of the ITT Population who fail to meet the specified PPEE criteria and, therefore, do not prequalify for the primary efficacy endpoint.

- 4) The “Non-Drinker Population” – The subset of the ITT Population who are non-drinkers, as evidenced by 100% negative results for the presence of EtG in urine from the beginning of screening through the urine test on Study Day 8, prior to randomization and 2) consistent self-report of no alcohol use throughout this same period of time, as well as the 30 days prior to screening.
- 5) The “Attempting Alcohol Abstinence (AAA) Population” – The subset of the ITT Population who: 1) fail to meet criteria for the “Non-Drinker Population” and 2) commit to quitting drinking during the study, as evidenced by viewing the optional Quit to Quit module on Study Day 8 prior to randomization.
- 6) The “Baseline Low Use/Adherent Population” – The subset of the non-PPEE Population who failed to qualify for the primary efficacy endpoint only because they reported <8 days of cocaine use during the 30 days prior to screening (plasma acetazolamide level on Study Day 8 was  $\geq 15$  ng/mL).
- 7) The “Baseline Adherent Population” – The combination of the PPEE Population and the Baseline Low Use/Adherent Population (all subjects with Study Day 8 plasma acetazolamide levels  $\geq 15$  ng/mL).
- 8) The Baseline Non-Adherent Population – The subset of the ITT Population who are not part of the Baseline Adherent Population (all subjects with Study Day 8 plasma acetazolamide levels <15 ng/mL).

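### Exploratory endpoints (q) and (r) compare the arms within subsets formed after randomisation (Week 13 completion and Weeks 11-13 alcohol status), so they should be descriptive only

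*Combined protocol and SAP*

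**What the plan says.** Section 14.3.3 lists exploratory measures (a) to (cc). Endpoint (q) is the proportion abstinent from cocaine in Weeks 11-13 among PPEE subjects "who completed the Treatment Phase (remaining through the end of Study Week 13) and were abstinent from alcohol during the last three weeks". Endpoint (r) is the same proportion among PPEE completers who remained through Week 13 "and were NOT abstinent from alcohol during the last three weeks of treatment". For each, "Comparison of this proportion in subjects receiving lorcaserin vs. placebo will constitute the analysis". No test, purpose or caveat is given for either.

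Alcohol abstinence is also an outcome in its own right. The Synopsis states that "An important exploratory endpoint will focus on the efficacy of lorcaserin in facilitation of abstinence from alcohol", and endpoints (k) to (o) and (t) compare it by arm; (o), for example, is "The proportion of subjects successfully achieving abstinence from alcohol during the last three weeks of treatment (Study Weeks 11-13) in the ITT Population".

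The secondary endpoint (14.3.2) takes a different route. It uses PPEE subjects who belong to the Non-Drinker or AAA Population, and section 14.2 fixes both groups before randomisation. AAA subjects are drinkers who "commit to quitting drinking during the study, as evidenced by viewing the optional Quit to Quit module on Study Day 8 prior to randomization".

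**The concern.** Randomisation on Day 8 makes the arms comparable as randomised. It does not make them comparable within a subset that treatment can help to form. Bias in (q) and (r) needs two links, and the documents make both plausible.

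- **Drug to subset.** The protocol looks for a lorcaserin effect on alcohol abstinence and cites reduced alcohol self-administration in rats (3.4.3). An effect on completion is possible too: 3.4.7.1 reports slightly more discontinuations on lorcaserin for headache, depression and dizziness.
- **Subset to outcome.** Motivation plausibly drives both kinds of abstinence. There is also a shared data source. The device records the previous day's cocaine and alcohol use together (12.24), and both abstinence definitions require a self-report for every day. Days that are missed and not recovered can make a completer both not abstinent from alcohol and a cocaine failure.

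The two endpoints also remove non-completers from the denominator, whereas the primary rule counts dropouts as failures (14.3.1).

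What is at stake is interpretation. Set beside the secondary endpoint, (q) and (r) invite the statement that lorcaserin works, or does not work, in people who stop drinking. The design cannot support that statement from these subsets.

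**Working it through.** **The plan's own figure.** Section 14.1 gives 90 PPEE subjects per arm and 80% power, "Assuming 6% and 20% success rates (for achieving abstinence from cocaine) during placebo and lorcaserin treatment, respectively" (Pearson chi-square, two-sided alpha 0.05). With mean proportion 0.13:

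Power = Φ[(0.14 − 1.96·√(2·0.13·0.87/90)) / √((0.06·0.94 + 0.20·0.80)/90)] = Φ[(0.14 − 0.0983)/0.0490] = Φ(0.851) = 80.3%.

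This reproduces. The documents give no figure for (q) or (r), so everything below except the 90 per arm and the 6% and 20% rates is assumed.

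**Model 1: two classes, no lorcaserin effect on cocaine use.** Assumed: 30% motivated and 70% less motivated; completion 80% and 60%; cocaine abstinence among completers 20% and 2.86%; placebo alcohol abstinence 60% and 20%. Overall success is 0.3·0.8·0.20 + 0.7·0.6·0.0286 = 6.0% in both arms.

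Subset rate = Σ(share · completion · alcohol status · cocaine abstinence) / Σ(share · completion · alcohol status).

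Worked case: lorcaserin raises alcohol abstinence only in the less motivated, from 20% to 45%.

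- (q) placebo: (0.0288 + 0.0024)/(0.144 + 0.084) = 13.7%
- (q) lorcaserin: (0.0288 + 0.0054)/(0.144 + 0.189) = 10.3%
- (r) placebo: (0.0192 + 0.0096)/(0.096 + 0.336) = 6.7%
- (r) lorcaserin: (0.0192 + 0.0066)/(0.096 + 0.231) = 7.9%

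| Assumed drug effect on alcohol abstinence | (q) placebo vs lorcaserin | Difference | (r) placebo vs lorcaserin | Difference |
|---|---|---|---|---|
| None | 13.7% vs 13.7% | 0 | 6.7% vs 6.7% | 0 |
| Less motivated only (20% to 45%) | 13.7% vs 10.3% | -3.4 | 6.7% vs 7.9% | +1.2 |
| Both classes (to 80% and 40%) | 13.7% vs 12.0% | -1.7 | 6.7% vs 5.6% | -1.1 |
| Motivated only (60% to 90%) | 13.7% vs 15.2% | +1.5 | 6.7% vs 4.0% | -2.7 |

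Alcohol effects alone can therefore give either sign in either endpoint.

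**Model 2: continuous shared factor U ~ N(0,1).** Cocaine logit = a + cU, with a set to give 6%. Alcohol logit = -0.8 + cU + b on lorcaserin, which gives placebo alcohol abstinence of about 34-36%. With b = 0.5 or 1.0, c = 1.0 or 1.5, and completion not modelled:

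- (q) difference: -0.65 and -1.22 (c = 1.0), -1.13 and -2.08 (c = 1.5).
- (r) difference: -0.3 to -0.7.
- If the planned 6% to 20% effect is real, (q) shows 16.1-19.7 points against 19.0-22.2 with the subset composition held as on placebo, and (r) shows 6.9-10.5 against 9.3-11.4.

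**Model 2 with completion instead.** No alcohol effect; placebo completion 60-80%; completion log-odds ratio -0.5 to -1.0 on lorcaserin; a reset so that placebo success with dropouts as failures is 6%. The differences become +0.3 to +1.9 in (q) and +0.3 to +1.1 in (r).

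**Sampling error.** SD = √[p₀(1−p₀)/n₀ + p₁(1−p₁)/n₁], with n the expected subset size. In the worked case of Model 1, n is about 20.5 and 30.0 for (q), so SD = √(0.1369·0.8631/20.5 + 0.1027·0.8973/30.0) = 9.4 points.

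| No cocaine effect | SD in (q) | SD in (r) |
|---|---|---|
| Model 2, no dropout | 6.5-7.3 | 3.2-4.0 |
| Model 2, with completion | 8.7-11.7 | 4.4-7.8 |

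Both subsets require completion, so the second row is the more realistic.

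**The case against.** The strongest reply is that there is little to correct. Endpoints (q) and (r) are two of 29 exploratory measures, with no alpha, named test or causal claim. The opening of section 14 describes presentation by descriptive statistics, and the comparison sentence is repeated across most of the list. The alcohol question that ranks as secondary already uses a pre-randomisation subset. Every driver of the calculated bias is assumed, and the bias is smaller than sampling error. Finally, a Statistical Analysis Plan is mentioned to which details of several other measures are deferred, so the silence on a test or caveat holds only for the text available.

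Most of this stands, and it is why the point is minor. It does not remove the point. The text makes the lorcaserin-placebo comparison the analysis of (q) and (r), whereas (aa) is expressly descriptive and several other measures carry a note on purpose.

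It is also fair that viewing a module on Day 8 shows intention, not realised drinking. The baseline groups answer a neighbouring question, but one that randomisation supports.

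A reader might infer three stronger things that the documents do not support:

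- That the trial's main efficacy findings are compromised. PPEE, Non-Drinker and AAA status are set by pre-randomisation data. The only later exclusion is the ITT rule, "with the exception of any subjects who return the full bottle before leaving the clinic on Study Day 8".
- That the bias must run against lorcaserin. The models above give both signs.
- That false positives rise materially. No test is specified for these endpoints, and the assumed biases are small beside the SDs.

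**Conclusion.** The concern holds as a minor one. The contrasts in (q) and (r) are not protected by randomisation. They are unbiased if lorcaserin affects neither drinking nor completion. They can be biased if it affects either and these share causes with cocaine abstinence. The protocol's own interest in an alcohol effect makes that a live possibility.

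With no cocaine effect, the assumed models together give about -3 to +2 points in (q) and -3 to +1 in (r), against SDs of about 9-12 and 4-8 points with 60-80% placebo completion and lower completion on lorcaserin. Neither range is a bound: other assumptions would give other values. The consequence is limited to how these two results may be read. Endpoint (bb) shares the weakness because it requires a Week 13 value.

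**What to change.** In section 14.3.3:

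1. Report (q) and (r) descriptively by arm, with subset sizes, and state that no between-arm efficacy inference will be drawn. Attach the same caution to (bb).
2. For whether the cocaine effect depends on drinking, use all PPEE subjects as randomised, with dropouts as failures. Keep the secondary endpoint (Non-Drinker and AAA pooled). Add the treatment difference with a confidence interval in the remaining PPEE subjects, who belong to neither group. Give the difference between the two effects with its interval, as an estimate and not a test. Only the estimate in the remaining subjects and that difference are new.

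The cost is protocol and SAP wording plus one short analysis of data already collected. There are three drawbacks. The effect among alcohol-abstinent completers is no longer compared inferentially. Day 8 intention is not realised drinking. And the new estimate is imprecise. Suppose a 6% to 20% effect is confined to the pooled group, 6% applies otherwise, and that group is an assumed 50%, 60% or 70% of 90 per arm. The 95% half-width around the 14-point difference in effects is then 1.96·√[(0.06·0.94 + 0.20·0.80)/n₁ + 2·0.06·0.94/n₂] = 16.8, 16.6 and 17.1 points for n₁/n₂ of 45/45, 54/36 and 63/27.
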